Family Meal Observational	Parents and adolescents engage in a video recorded family	I,A,B		I,A,	I,A,	I,A,
Assessment	meal session involving conversation about the present meal	C,P		BC,	BC,	BC,
	and meals in the last week involving happiness, sadness,			Р	Р	Р
	anger, and fear. Recordings coded for parent coaching of adolescent emotions in response to meals.					
Weekly Homework Task	Parents are asked to practice their EC skills daily by having		BC			
Trookly Homowork Tuok	a 5-10 minute "de-briefing" of following select meals.					
	Recordings coded for parent coaching of adolescent					
	emotions in response to meals					
Encouragement of Behavioral Freedom ⁴⁴	Adolescent report of parental encouragement of behavioral freedom	Α		Α	Α	Α
Multidimensional Assessment of	Parent report of parenting behaviors including proactive	P		Р	Р	Р
Parenting Scale ⁴⁵	parenting, positive reinforcement, warmth, supportiveness,					
Background Questionnaire	hostility, lax control, and physical control. Parent report of family demographics	P	1	Р	Р	Р
-		۲		F	F	
Acceptability of Intervention Measure	Interventionist report of acceptability	1	I *	I	I	I
Intervention Appropriateness Measure	Interventionist ratings of intervention appropriateness	I	I *	I	I	I
Feasibility of Intervention Measure	Interventionist rating of feasibility of intervention	I	l*	I	I	I
Note. A = Adolescent, P = Parent	I = Interventionist, BC = Blind Coder, TD = Treatment development team, *only administered after session 5 of EC intervention					

Families will then be instructed to complete baseline assessment questionnaires online through RedCap. The baseline visit will be conducted via Zoom for Healthcare. Families will complete a family meal which will be recorded and later coded, and interviews. All families will be mailed an audio recorder to record future EC intervention homework at this time. Families will opt in for text message appointment reminders.

7. PROCESS OF OBTAINING CONSENT

Prior to study enrollment, permission from the attending adolescent medicine physicians of each eligible participant will be obtained in clinic. As noted above, once participants are identified as study eligible, they will be contact within 24 hours of an initial visit in the CCHMC Eating Disorders Program, during an in-patient stay via Jabber, or within 24 hours of their first therapy visit and provided a description of the study, including study procedures, benefits, and risks, by the trained study coordinator included on the approved IRB protocol. Due to face-to-face restrictions due to COVID-19, we will initially approach potential participants via phone after receiving permission from their physician and sending them a recruitment letter. They will be given an information sheet and asked to complete the FMSS over the phone. We are asking for waiver of documentation of consent to perform the FMSS as this is an eligibility criterion. The research coordinator will inform families of their eligibility within 2 days of the FMSS over the phone. At this time, informed e-consent and assent will be obtained from caregivers and adolescents and all questions asked by participants will be addressed. Adolescents will be explained the study in teen-friendly terms, so they understand study procedures. Participants will be explicitly informed that their care at CCHMC will not be affected whether they choose to participate in the study or decline participation.

8. STUDY PROCEDURES

This is a 6-month study of adolescents with AN and AAN and their caregivers. Study participants will complete assessment questionnaires at baseline, 1-month, 3-months, and 6-months. Participants will be randomized to either treatment or control conditions. They will engage in either 10 parent EC group sessions or 10 parent support sessions over a 3-month period followed by a post-treatment assessment (see Table 2).

Measures: At each time point, caregivers will complete self-report measures of satisfaction with the intervention, parenting behaviors, psychological functioning, levels of EE, levels of warmth, and strategies for managing adolescent negative emotions (60 minutes to complete; see Table 2). Adolescents will be assessed for their level of AN or AAN symptoms using the gold standard for AN assessment; the EDE. Adolescents will also report on parenting behaviors and their own psychological functioning. These questionnaires best assess the constructs of interest and have good reliability and validity in pediatric AN population. The mechanisms of treatment outcome that we are testing are high EE and parental warmth, which will be assessed by the FMSS and family meal at each time point. Our outcome is adolescent weight restoration (≥ 95% expected body weight [EBW]). Based on prior literature, demographic, medical, and behavioral covariates including socioeconomic status, adolescent behavioral functioning, caregiver burden, and caregiver psychological and emotional functioning will be assessed in the current proposal.

9. DATA ANALYSIS / METHODS

Exploratory Aim: Examine whether the FBT+EC parent group intervention reduces EE, increases parental warmth, and improves weight restoration in the RCT. H1a. We will have preliminary evidence that families in the FBT+EC group will have lower levels of EE and higher parental warmth than families in the FBT+support group at 1 month which will be sustained at 3 and 6 months. H1b. We will have preliminary evidence that EE and parental warmth are correlated with weight restoration at 1, 3, and 6 months. H1c: We will have preliminary evidence that adolescents in the FBT+EC group will demonstrate improvements in weight restoration compared to children in the FBT+ parent support group at 1, 3, and 6 months.

Exploratory Analyses: All analyses will be carried out with missing data assumed to be missing at random and handled via maximum likelihood estimation with auxiliary correlates⁶⁸ within Mplus (Version 8) on the full sample (N=50). Bivariate correlations will first be calculated among EE, parental warmth, and weight restoration (measured continuously as mean percentage of EBW) at 1, 3, and 6 months (H1b). To test whether families in the FBT+EC group will have lower levels of EE and higher parental warmth (H1a) as well as greater improvements in weight restoration (H1c) than families in the FBT+support group, 3 separate ANCOVA models will be used to test our hypotheses for each outcome. Baseline measures of EE, parental warmth, parental psychopathology, length of illness, and %EBW will be included in the models as control covariates.

Power: Although a pilot trial, Monte Carlo simulation power calculations showed that, assuming N=50, power will be \geq .80 for between group difference effects of $d \geq 1$ for all outcomes (EE, parental warmth, weight restoration), assuming both standardization of analysis variables and baseline covariates (EE, parental warmth, parental psychopathology, length of illness, and %EBW), which will explain ($R^2 = .35$) 35% of response variable noise variance.

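### H1b pools both arms with no arm term, so its correlations with weight can partly reflect allocation if EC also reaches weight by another path

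*Combined protocol and SAP*

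**What the plan says.** Section 9 (Data Analysis / Methods) states H1b as preliminary evidence that "EE and parental warmth are correlated with weight restoration at 1, 3, and 6 months". The method is one sentence: "Bivariate correlations will first be calculated among EE, parental warmth, and weight restoration", with weight "measured continuously as mean percentage of EBW". All analyses are to use the full sample of 50. The section mentions no arm term, partial correlation or within-arm estimate for this step. The baseline covariates are attached to the ANCOVA models for H1a and H1c.

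The neighbouring hypotheses expect arm differences on both sides of the correlation. H1a expects that "families in the FBT+EC group will have lower levels of EE and higher parental warmth than families in the FBT+support group". H1c expects that "adolescents in the FBT+EC group will demonstrate improvements in weight restoration compared to children in the FBT+ parent support group".

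Section 8 (Study Procedures, Measures) adds: "The mechanisms of treatment outcome that we are testing are high EE and parental warmth". No mediation model is specified, so H1b is the only planned analysis that links EE or warmth to weight.

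**The concern.** When two groups with different means on both variables are pooled, the difference in means adds to the covariance. If EC families end with lower EE and higher %EBW, the pooled EE-weight correlation is pushed negative and the warmth-weight correlation positive, whatever happens within the arms. The push is always in the hypothesised direction. Randomisation makes arm independent of baseline, so adjusting for baseline %EBW would not remove it.

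This is confounding only if arm reaches weight by a path outside the variable being correlated. The plan leaves room for one. Under Treatment Condition in Section 4, EC parents hold a daily debriefing with the adolescent after selected meals or snacks, receive weekly written feedback, and get role play and live coaching. None of this is described for the support group. The plan also names two mechanisms, so a weight effect carried by warmth is a path outside EE, and the reverse.

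At stake is how H1b is read. If H1a and H1c both succeed, H1b may partly restate them while appearing to be separate support for EE and warmth. Section 11 expects the data to inform further work on EC, so that reading could carry forward.

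**Working it through.** **Inputs.** 25 per arm (Section 4); N = 50 and d of at least 1 on EE, warmth and weight, with baseline covariates explaining 35% of variance (Section 9, Power). Assumed, because the documents do not say: two-sided .05 test, roughly normal variables, equal SDs in the arms, no dropout.

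**The plan's own figure.** Section 9 states power of at least .80 at d = 1. By the normal approximation:
- No covariate gain: 1/sqrt(2/25) = 3.54, and 3.54 - 1.96 = 1.58, so power is .94.
- R² = .35: the residual SD is sqrt(.65) = .806; 3.54/.806 = 4.39, and 4.39 - 1.96 = 2.43, so power is .99.

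The stated bound holds. It says which effect could be detected, not which is expected.

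**Formula.** Let arm shift EE by -d1 and %EBW by +d2 (within-arm SD units, 1:1 allocation), with within-arm correlation rw. Then

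pooled r = (rw - d1·d2/4) / sqrt[(1 + d1²/4)(1 + d2²/4)]

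With rw = 0:
- d = .5 on both: -.0625/1.0625 = -.06
- d = .8 on both: -.16/1.16 = -.14
- d = 1 on both: -.25/1.25 = -.20
- d = 1 on EE, .5 on weight: -.125/sqrt(1.25 × 1.0625) = -.11
- d = 1 on one variable, 0 on the other: 0

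**Rejection rates.** Simulation of 40,000 trials per setting, comparing the pooled test (48 df) with the partial correlation given arm (47 df):

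| d on EE | d on weight | rw | pooled r | pooled p<.05 | arm-adjusted p<.05 |
|---|---|---|---|---|---|
| .3 | .3 | 0 | -.02 | 5% | 5% |
| .5 | .5 | 0 | -.06 | 7% | 5% |
| .8 | .8 | 0 | -.14 | 16% | 5% |
| 1 | .5 | 0 | -.11 | 11.5% | 5% |
| 1 | 1 | 0 | -.20 | 29% | 5% |
| 1 | 0 | 0 | 0 | 5% | 5% |
| 1 | 1 | -.30 | -.44 | 92% | 57% |

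The last row shows inflation of a real association. With 20 per arm, the 29% becomes 24%. If the plan's d = 1 is in residual SD units, it is about .81 in the total SD units of a raw correlation, which brings the rate to about 16%.

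**When arm is not a confounder.** Suppose EE carries the whole arm effect: rw = -.30, d1 = 1, so d2 = .30 × 1 = .30. The pooled covariance is -.30 - .30/4 = -.375 and the pooled EE variance is 1 + 1/4 = 1.25. The pooled slope is -.375/1.25 = -.30, equal to the within-arm slope. The correlation moves only to -.375/sqrt(1.25 × 1.0225) = -.33, because EE is more spread out.

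**Price of adjusting.** With no arm effects, power is .57 adjusted against .58 pooled at rw = -.30. At r = -.58 it is .996 either way; -.58 corresponds to the 34% of variance that Section 3 gives as the upper value.

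**The case against.** The strongest reply is that the plan's theory has EC improving weight through EE and warmth. If EE carries the whole effect, arm is not a confounder and the pooled slope is right. This stands. A reader might infer that H1b is an artefact whenever H1a and H1c are both true; the documents do not support that, because a path around the correlated variable is also needed.

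Three other stronger readings also fail:
- *Extra contact as the other path.* Section 4 gives controls 10 support sessions and identical FBT, and calls the arm an attention control. The meal-linked homework and coaching are the more plausible difference.
- *29% as the plan's expected error rate.* It needs d = 1 on both variables and no within-arm association, and d = 1 is a detectability threshold. At d = .5 the excess is two percentage points.
- *The protocol presents H1b as proof of mechanism.* It does not. H1b claims only preliminary evidence of correlation, sits under an exploratory aim and has no alpha or decision rule. A pooled correlation answers that wording literally. The link to mechanism comes from the sentence in Section 8 and the absence of any other analysis that could address it.

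Nor would adjustment settle mechanism. Same-visit correlations are between families, and reverse causation and other confounding remain.

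What survives is narrower: a foreseeable bias, always in the hypothesised direction, in the only planned link between the named mechanisms and weight.

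**Conclusion.** The point holds as a limited refinement. As written, H1b cannot separate an association within arms from one produced by allocation, provided EC moves both variables and reaches weight partly by another path. The size depends on effects not yet known: negligible at d = .5 or below on both variables, and material at .8 to 1, where 16% to 29% of trials would show a significant pooled correlation with nothing behind it within arms. These rates are per correlation, and H1b has six (two variables at three visits). They rest on the assumed two-sided .05 test and on normality; if EE is scored as a count or category, the figures change but the direction does not. Priority is low to moderate.

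**What to change.** In Section 9, state that H1b will be reported at 1, 3 and 6 months as correlations adjusted for randomised arm (partial, pooled within-arm) with confidence intervals. Show arm-specific correlations descriptively and keep the pooled value as a secondary description. Add that the pooled correlation is not evidence of mechanism, and that the adjusted one removes only the allocation artefact and does not establish mediation.

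The cost is a few sentences, one added variable and one degree of freedom (48 to 47), with the negligible power loss shown above. No new data are needed. With 25 per arm the arm-specific values will be imprecise, which is why they should be descriptive only.

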10. FACILITIES AND PERFORMANCE SITES

Recruitment and all study assessments will be conducted at CCHMC. Due to face-to-face restrictions related to COVID-19, our initial efforts of study recruitment and study visits will be conducted over the phone and/or via Zoom for Healthcare which is HIPAA compliant. Data management will occur at CCHMC. Slack will be used as a data management tool between investigators at CCHMC and UGA. No protected health information will be shared over Slack. All study videos will be coded by Co-Investigator [name] at University of Georgia. Video recorded sessions will be transferred onto OneDrive, a secure drive on the CCHMC network. [name] laboratory at UGA has the capacity to transfer digital video and audio to secure computers and DVD burners for secure physical storage of video data, supported by departmental and college IT services. Secure wireless connectivity is available. A dedicated electronics shop is provided by the University to perform routine computer repairs and software support is available from a full time information technology (IT) support person dedicated to this department. The combination of these information technologies contributes to the potential for success by assuring both efficient data handling and optimal communication among the research team.

11. POTENTIAL BENEFITS

Participants in this study may benefit from improved family communication and eating disorder symptoms. The study is anticipated to support preliminary efficacy of an EC parent skills group as an adjunct to FBT. This could lead to improvements in several outcomes for patients who receive the EC intervention, including reductions in expressed emotion, and improvements in weight restoration. These data could support continued research to refine and adapt EC interventions for adolescents with AN and AAN and their families.

12. POTENTIAL RISKS, DISCOMFORTS, INCONVENIENCES, & PRECAUTIONS

This is a minimal risk study, a risk that is no greater than that encountered in routine behavioral assessment and clinical care. There are no medical risks to study participation. All the questionnaires, measures, and interviews have been used in research, including our own, without any reported negative effects; however, it is possible that a small group may feel uncomfortable responding to questions or being observed during a family meal interaction.

Several precautions will be taken to minimize the risk, discomforts and inconveniences associated with this study protocol. In the unlikely event that adolescents and their families feel uncomfortable answering questions, they are free to skip questions or questionnaires. Families may prefer to not be videotaped for their assessments and they are free to opt out of recording. Since the EC intervention is a group, all efforts to maintain confidentiality will be made but cannot be guaranteed in a group setting. All participants will learn about the group and the importance of maintaining confidential information inside of the group setting. Outside relationships will be discouraged. Families may also be inconvenienced by scheduling and attending intervention sessions. If the adolescent or caregiver is particularly distressed, appropriate treatment and or referrals can be made by the PI, who is a licensed clinical psychologist. Notably, because a trained therapist will be interacting with participants, there is the possibility that confidential information will be discussed. All sessions will be audio recorded to ensure treatment fidelity and will be erased after review by the Research Team. See section 14 and 15 regarding how this will be handled.

If any adverse reactions or complications occur as a result of this study, we will report them per CCHMC policy.

13. RISK/BENEFIT ANALYSIS

There is minimal risk associated with study participation. Knowledge gained in this study has the potential to improve the treatment of pediatric AN and AAN by increasing parent emotion coaching skills and decreasing expressed emotion, which would improve weight restoration outcomes in this population.

14. DATA SAFETY AND MONITORING

We expect this study to be no more than minimal risk to participants. The research team will monitor for safety and adverse events at each study visit. Specifically, intervention session content will be discussed in weekly supervision by the interventionist with [name], study Co-I. The interventionist and research study coordinator will also complete protocol checklists for treatment integrity and fidelity. The research study coordinator will review questionnaires for completion and review of items related to significant distress or suicidal ideation. We have procedures in place to ensure that the research coordinator checks these items immediately after completion of the measure and if the items indicate risk, a clinical psychologist either with the eating disorder team or the PI are notified immediately to assess for further risk.

If desired, administration of the assessment measures and participation will be discontinued at parent or patient request. The study team will provide referrals as appropriate for treatment needs resulting from significant adverse events or psychological issues that exceed the scope and/or intensity of the intervention. Adverse events will be reported to the CCHMC Institutional Review Board (IRB) during continuing review, while serious adverse events will be reported to the IRB within 24 hours.

15. PRIVACY AND CONFIDENTIALITY

We will also monitor adolescents for any adverse events per our Institutional Review Board (IRB) procedures and guidelines. Raw hard data will be stored in locked areas in the Division of Behavioral Medicine and Clinical Psychology and only authorized staff will have access to the computer files. Access to original data and study materials will be limited to the investigative team. All raw data, including questionnaires and computer files containing data will have confidentiality protected with the use of unique assigned study identifier codes; computer files will be password protected. A master file linking the identifying patient information with the study ID code will be secured in a password protected file. This master file will be destroyed upon

completion of the study. Data will be retained until final data analyses are completed; all deidentified data will then be shredded and destroyed. Neither names nor identifying information will appear in any publication based on this research. All audio files will be password protected and then deleted after they have been reviewed by the PI for treatment fidelity.

Confidentiality will be retained throughout the study related to intervention content, with one exception. If the participant provides information about something that might put the participant or another person in danger, we are obligated to report this as mandated reporters. This will be shared in the consent/assent form.

All study personnel have been trained in data safety and monitoring, privacy and confidentiality, minimizing risks related to loss of privacy and confidentiality. We will closely monitor performance of our research personnel to ensure the strictest standards. Study personnel will screen questionnaires for completeness and participants will be encouraged to complete missing items. If there are any elevations on risk-items, the PI will be immediately notified and will ensure that risk is assessed by either a licensed psychologist or a master's level licensed therapist. Data from each questionnaire will be entered into a Redcap database and then analyzed with SAS, Mplus, or SPSS.

Because this research study involves payment for participation, we are required by Internal Revenue Service (IRS) rules to collect and use participant's social security number (SSN) or taxpayer identification number (TIN) in order to track the amount of money that we pay them. Unless they have given specific permission for another use of their SSN or TIN related to this research study, we will only use their SSN or TIN to keep track of how much money we pay them and their SSN or TIN will not be used as part of this research study.

16. COST OF PARTICIPATION

There are no costs for participation in this research study. Participants will be responsible for the usual costs of medical care.

17. PAYMENT FOR PARTICIPATION

Participants will complete 10 EC group sessions, baseline assessments, and post-treatment assessments. Adolescents can earn \$100 and caregivers \$100 for their participation (\$25 at each of the 4-assessments). Families can choose to have separate ClinCards or can be paid on one ClinCard together. If they miss one of the 4 assessments, they will not be paid for the one they miss.

We will give participants their payment in the form of a reloadable debit card (ClinCard) and they will receive a handout that will explain how to use this card. We will provide them with a card, and we will load money onto their card after completion of the baseline visit and after completion of the post treatment visit.

